1. FUNDING SECURED			
Australian Respiratory Council 2006 grant	Medications,	April 2008	40 000
	Sputum,		
	consumables		
In-kind support from existing resources at	Materials		unspecified
field site (NHMRC Project grant)			
Major in-kind contributions pledged by out-	Materials, travel,	Pre-June 2008	unspecified
going MALKON director.	in-kind support for		
	clinical staff wages		
PhD student scholarships and bursaries			
1 [name]			
Australian National University:	Travel / Materials	2008-2010	11 750
Fieldwork Funding Supplement and			
NCEPH grant			
Endeavour Fellowship	Travel, living costs	2008	20 000
	at Research centre		
	in Timika		
RACP Covance Fellowship	Material costs	2008	20 000
2 [name]			
AusAID scholarship	Materials and travel	2007-2011	70 000 *
Australian National University			To be advised
Timika local health office			To be advised
2. APPLICATION / ASSESSMENT PEND	DING	1	
Australian Respiratory Council 2008 grant	Short-listed for 2008 award. To be		51 000
	officially notified Fe	bruary 2008	
National Health and Medical Research	Application to be sub	To be advised	
Council			

* includes PhD scholarship and tuition fee

12 PUBLICATION POLICY

The study results will be published by the investigators with acknowledgement of the funding bodies. All co-investigators will be offered authorship according to their involvement in the study and

conforming with standard international definitions for authorship (83). An accurate list of publications to arise from the research cannot be clearly anticipated until research is underway. Possible outputs with identification of assigned researcher and key authors are listed below (Table 5). During the course of the project, there may be changes, which will be agreed upon by mutual agreement of NIHRD & MSHR, to both the list of investigators involved (e.g. in the event of transfer of investigator elsewhere, or requirement to seek further expertise from statisticians or other consultants), and to publications arising.

Research assistants and clinicians at the study site whose work is integral to the research will have the opportunity to be included as authors on publications as appropriate based on international standards of contribution (as in previous publications to date arising from the Timika NIHRD-MSRH research collaboration). NIHRD and MSHR endorse the internationally recognised requirement that first authorship requires leadership of the work involved in each paper (ie considerable ownership and leadership with regard to study design, analysis, writing the paper and major intellectual input to the paper). Co-authorship will apply for all who significantly contributed to the work, in keeping with international standards of authorship (i.e. input to study design and/or data collection and/or analysis as well as a substantial intellectual input to the paper).

Table 5: Researcher	Responsibilities ar	nd Publication Pl	an Proposal
---------------------	----------------------------	-------------------	-------------

Study		Publication topic	Researche	r Responsible	Planned main
		Each listed topic does not necessarily represent a single publication but may be split into separate manuscripts or amalgamated with others depending on results obtained	NIHRD	MSHR	author
ADAPT	RCT	Validation of a composite clinical endpoint for an assessment of TB severity Correlation of Arg/vit D/NO /other parameters with markers of TB severity: baseline and longitudinal. RCT outcomes and relationships	[name] [name]	[name] [name] [name]	[name]
		Trends in drug resistance in Papua	[name]		[name] /[name]/ WHO Ref Lab
		TB genotype and ethnicity	[name] [name]		[name] /[name]
		T-cell function in TB	[name]	[name]	[name]
	Economics	Cost effectiveness of vit D & arg	n/a	[name]	[name]
	Nutrition	Nutritional status of TB patientsOther nutritional topics to be confirmed	[name] & colleagues	[name]	[name]
	PK/PD	Arginine pharmacokinetics / pharmacodynamics (embedded into pre-existing study design)	[name]	[name]	[name]/[name]
EPTB		Diagnosis, ethnicity, treatment outcome & disability	[name] [name]	[name] [name] [name]	[name] / [name]
Controls		Vit D/Arg normal values in Papua by ethnicity, nutritional intake & UV	[name] [name]	[name] [name] [name]	[name]/[name]
Rapid diagnostic test		Test characteristics on field testing in Papua	[name]	[name] [name] [name]	[name] / TBC*
HIV/TB		Descriptive epidemiology including manifestations of HIV-TB (e.g. proportion with EPTB) Factors associated with HIV-TB related morbidity Other topics to be developed	[name]	[name] [name] [name]	[name]
Economic		Active case finding in a high burden country Economic burden of TB in Papua Cost-effectiveness of active vs passive case finding	n/a**	[name]	[name] [name] [name]
Other		Enhanced public/private partnership & standards of TB care in Timika TB control	[name]	[name]	Timika clinician

*TBC: to be confirmed. Negotiation with Proteome Diagnostic company will be required regarding authorship **n/a = not applicable. [name] is an Indonesian PhD scholar based at ANU.

Appendices A

13 APPENDICES A: Details of study methodology

Appendix A comprises Appendices 1 to 18.

Appendix 1: BASELINE DATA COLLECTION FORM

(inserted hereafter)

ADAPT		Code	• TAD-		
BART HE		ENGUMPULAN DATA DASAR ollection form / Module P1	school of health resear		
		Nama Peserta udy Participant name			
1. Tanggal hari: Date today	/	/20_ _			
2. Nama [pertama First Name]:				
3. Nama [keluarga Surname	ı]:				
			Code		
4. Tempat: TB C Enrolment Site RSM Pusk Othe	M 2 cesmas 3	Papuan TAD-1000s TAD-3000s TAD-5000s TAD-7000s	Bukan Papuan TAD-2000s TAD-4000s TAD-6000s TAD-8000s		
X		ata Pewawancara nterviewer's details			
5. Nama pewawar Data collector					
6. Waktu muliai w Time interview commence					
7. Waktu selesai v Time interview ended	wawancara :/ hr min	l			

Tolong tuliskan no. kartu TB dari respondent yang bersangkutan disetiap halaman formulir ini Please write the code number on the participant's TB card and on every page of the data collection form

ADAPT		Code TAD-	
	Bagain C: Kriteria Inklusi dan Ek Section C: Inclusion and Exclusion Criter	s klusi ia	
8.	BTA positif TB paru: Smear positive pulmonary TB	Ya 🗌	Tidak 📃 2
9.	TB Baru: Never treated for TB before	Ya 🗋	Tidak 🗋 2
	Bersedia untuk menjalani pengobatan d nika selama 6 bulan: e to continue treatment in Timika for 6 months	i Ya 🗖	Tidak 🗌 2
11. Age :	Umur > 15 th: >15yrs	Ya □₁	Tidak 🗌 2
	Persetujuan Consent untuk partisipasi dalam penelitian ini: ent given	Ya □₁	Tidak 🗌 2
В	ila menjawab "tidak" untuk pertanyaan no dimasukkan dalam peneliti If 'No' to any questions 1 to 5, PATIENT IS N	an ini.	tidak bisa
13. Pregr	Apakah dalam keadaan hamil ?	Ya 🗌	Tidak2
14.	lonized calcium > 1.32 mmol/L?	Ya 🗌 1	Tidak 📃 2

Bila pasien menjawab "Ya" untuk pertanyaan no. 6-7, pasien tidak bisa diikutkan dalam penelitian ini. If 'Yes' to question 6-7, PATIENT IS NOT ELIGIBLE

Code TAD- |__|_|_|

Bagain D: Informasi dasar peserta Section D: Respondent Baseline Information

15. Tanggal kelahiran: Date of birth: dd/mm/yyyy	/ /19	
16. Umur:tahun_ Age yr	bulan mo	
17. Alamat : Address		
18. Telepon : Phone		
19. Jenis Kelamin: Sex: M1,F2	_aki □₁ Per	rempuan 🔤 ₂
 20. Nama Kepala Rum Tangga: Name of head of household 21. Kode rumah tangg Household code 		_
22. Suku: Ethnicity	Papuan □₁ Buk	$an Papuan \square_2$
22a. Bila Papuan:	Dani \square_2 Origin: h'la Moni \square_3 [erah asal: and1 / l'land2 Daerah pegunungan1 Daerah dataran2
23. Pendidikan terakh Education: (Primary1, High2, Fur		
24. Riwayat merokok?	Merokok Pernah merokok tetapi su	

ADAPT		e TAD- _ _
	000	
Smoker? 24a. Jika merokok, cigs/day?	Tidak pernah merokok Berapa banyak rokok yang diisap p hari ?	er / hari bulan
25. Sudah berapa lar How long have you have this s		
	gian E Keadaan Perilaku Pengobat ction E: Employment and Treatment-seeking behavio	
26. Apakah pekerjaan ya What work would you ha	ang sedang anda kerjakan: ve been doing:	
Bekerja di pertani Bekerja di rumah Pergi ke sekolah Berlibur Leisure time	Working at home Going to school Jika "Tidak Ada", lanjutkan ke pertanyaan nomor	$ \begin{array}{c} 1 \\ 2 \\ 3 \\ 4 \\ 5 \\ 29 \\ 6 \\ 7 \end{array} $
bekerja?	nendapatkan upah, berapa anda dibayar	untuk satu hari
aktivitas rutin (beke	-	ı mengerjakan seluruh
hari	nable to perform all of your usual activities (work/school)?	
sebagian aktivitas r	thir berapa jumlah hari anda hanya mamp utin (bekerja / sekolah)? ble to perform some of your usual activities (work/school)?	ou mengerjakan
30. Apakah anda menca Did you seek treatment?	ari pengobatan? Ja Tidak	2
30a. Jika "Tidak", apa If "No", what is the reason		

Code TAD- |__| I

Tidak punya biaya untuk berkunjung No expense to pay a visit	1
Tidak ada sarana transportasi No transportation	2
Tidak ada biaya transportasi No transportation expense	3
Obat dan peralatan tidak memadai Drug and equipments are not be adequate	4
Ketrampilan petugas tidak memadai Skill worker is not be adequate	5
Pernah mendapatkan pelayanan yang buruk Have got bad services	6
Penyakit tidak terlalu berat Disease do not too severe	7
Lainnya, sebutkan Other, specify	8
31. Dimana anda menerima pengobatan dan bagaimana urutannya? Beri nomor se	suai

[figure not shown]
urutan konsultasi

Where did you receive treatment and in what order? Put number in order of consultation

No	Uraian Description	Beri nomor sesuai urutan konsultasi Put number in order of consultation	Berapa kali pasien pergi How many times did patient go to
1	Pengobatan Tradisional di rumah Home traditional remedy		
2	Pengobat tradisional Traditional healer		
3	Obat di rumah atau dari tetangga Drugs from home or neighbour		
4	Klinik / Dokter Swasta Private Clinic / Doctor		
5	Apotik Pharmacy		
6	Toko Obat Shop		
7	Puskesmas / Pustu Public health center		
8	Klinik TB PHMC Clinic		
9	Rumah Sakit Hospital		

Bagain F : Sakit Lain-Iain

32. HIV test: Positif1	Negitif 2		
32a. Bila positif: tan	ggal diagnosis	1 1	
Approximate diagnosis date		_ I I	
32b. Apakah anda m	ninum obat untuk HIV	V?	
Taking medication for HIV?			
Ya 🗌 1	Tidak 📃 2		
32c. Obat apa?		D4T	
What medicines?		3TC	\square_2

Appendix 2: WEEKLY DATA COLLECTION FORM

	Study fille Number 07740	
ADAPT	C	ode TAD- _ _ _
BARTY HUSS	FORMULIR PENGUMPULAN DATA MINGGUAN Weekly data collection form	school of health research
	Lembar 1 : Data Peserta Page 1: Participant Identification	
1. Nama [pertama]: _ First Name		
2. Nama [keluarga]: surname		
3. Alamat baru bila ada New Address if changed	perubahan:	
4. Tanggal hari: Date today	20	
5. Minggu pengobatan: Week of treatment (range: 0-2	(Minggu pendaftaraan = 0; minggu pen 4. Enrolment Week = 0)	gobatan 0 – 24)
	Bagain B : Data Pewawancara Section B: Interviewer's details	
6. Nama pengumpul Data collector	data :	
7. Waktu muliai waw Time interview commenced	vancara :/ hr min	
8. Waktu selesai way Time interview ended	wancara :/ hr min	

Code : TAD- |__|_|_

Tolong tuliskan no. kartu TB dari respondent yang bersangkutan disetiap halaman formulir ini

Bagain C: Tabel Pemeriksaan Mingguan

Section 3: Table of Weekly Testing Required

'X' pada kolom abu-abu berarti pemeriksaan tidak perlu dilakukan dalam minggu tersebut. Pemeriksaan perlu dilakukan pada kolom yang kosong. Lingkari kolom 'pengobatan minggu ke ... ', contoh : minggu 0 = minggu pertama

'X' in grey box means test not required that week. Circle which week of treatment the patient is up to (Week 0 = first week).

Pengobatan	Tanyakan	Kirim dahak	Kirim	Ambil	Periksa	Periksa	Tes	Kuesioner	Foto
minggu ke	gejala-	untuk	dahak	darah	NO	Fungsi	jalan 6	St George	Rontgen
	gejala	pemeriksaan	untuk			Paru	menit		dada
		mikro	kultur						
Which week?	Ask about	Send sputum	Send	Collect	Meaasure	Do lung	Do 6	Do SGRQ	Do Chest
	symptoms	for micro	sputum	blood	exhaled	function	minute		x-ray
			for		NO	tests	walk		
			culture				test		
0									
1			Х	Х	Х	Х	Х	Х	Х
2			Х			Х	Х	Х	Х
3			Х	Х	Х	Х	Х	Х	Х
4									Х
5			Х	Х	Х	Х	Х	Х	Х
6			Х	Х	Х	Х	Х	Х	Х
7			Х	Х	Х	Х	Х	Х	Х
8									
12		Х	Х	Х	Х	Х	Х	X	Х
16		Х	Х	Х	Х	Х	Х	X	Х
20		Х	Х	Х	Х	Х	Х	Х	Х
24			Х						

Code : TAD- |__|_|_|

Tolong tuliskan no. kartu TB dari respondent yang bersangkutan disetiap halaman formulir ini

Bagain 4 : Petunjuk Langkah Demi Langkah Pengkajian Mingguan

Section 4: Step-by-step guide to weekly assessments

				Instrucsi para pengumpul data
9. Jam berapa maka How long ago did patient last ea			Jam yang Ialu	Berikan dosis pengobatan TB dengan supervisi Give supervised TB medication dose
10. Selama minggu berapa kali minum During the last week, how many	obat TB?		0	
During the last week, now many			2 3 4	
			5 6	
		7	7 Don't know	
11. Waktu pengam (dicatat juga di tab What time was blood taken (writ	ung)	:8	jam	Minggu 0,2,4,8,24 : ambil darah Weeks 0,2,4,8,24: take blood
12. Catat hasil pen	neriksaan darah i	STAT:		
Write iSTAT blood results	Ionised calcium		mmol/L	
	Creatinine		mmol/L	
	Haemoglobin		g/dL	
13. Jika ada hasil p relevan:	pemeriksaan dara	ah yang		Ingat !! penyimpanan sampel darah
If any other relevant / abnormal	blood tests are available, wri Uric acid	te results here:	mg/dL	Keep remainder of blood for storage * record any adverse events
	ALT		u/L	
	Other			
	Other			
	Other			

[figure not shown]
Code : TAD- |__|_|_|

Tolong tuliskan no. kartu TB dari respondent yang bersangkutan disetiap halaman formulir ini

14. BTA AFB	$ \begin{array}{c} 1 \\ 2 \\ 3 \\ 4 \\ 5 \\ 6 \end{array} $	0 Scanty 1+ 2+ 3+ 4+	Setiap minggu sampai minggu ke 8, dan minggu ke 24, Pemeriksaan dahak mikroskopis Every week until week 8, then week 24, collect sputum for microscopy and indicate result
15. eNO: jam		ppb	Minggu 0 , 2 ,4, 8, 24: Periksa NO dan tulis hasil
16. Selama minggu lalu, berapa kali minum obat sirup During the last week, how many doses of study medication were taken?	$ \begin{array}{c} 0\\ 1\\ 2\\ 3\\ 4\\ 5\\ 6\\ 7\\ 7 \end{array} $	0 1 2 3 4 5 6 7 Don't know	Berikan makanan ringan kepada pasien Give patient a snack Berikan pengobatan studi (obat sirup setiap minggu mulai minggu 0 – 8, obat tablet hanya pada minggu 0 dan 4) Give study medications (arg every week, D only week 0 and 4)
17. Berat badan		kg	
18. Height		m	Omit if already done in previous week and not
 19. Tes jalan 6 menit ^{6-min walk test} 20. Tes fungsi paru 		m	growing MINGGU 0,4,8,24: Lakukan tes jalan 6 menit dan catat jarak tempuh jalan: Weeks 0,4,8,24 : Do 6-min walk test Lakukan tes fungsi paru
Lung function tests		L/s	dan catat hasil
FVC		L	
21. Kuisioner Respiratori St George	Ya 🗌 1	Tidak 📃 2	MINGGU 0,4,8,24: Interview and isi kuisioner Respiratori St George
SGRQ done yes / no 22. Foto rontgen	Ya 🗌	Tidak 🗌 2	MINGGU 0,8, 24: CXR

Code : TAD- |__|_|_|_

Tolong tuliskan no. kartu TB dari respondent yang bersangkutan disetiap halaman formulir ini

NIHRD_MSHR Health Research Collaboration ADAPT study Study HREC Number 07/40

ADAPT	•	e : TAD- _	_
Tolong tuliskan no. kartu TB dari respondent yang ber	sangkutan dise	etiap halaman form	ulir ini
Gg. Pendengaran	Ya 🗌	Tidak 🔤 2	
Gangguan penglihatan	Ya 🗌	Tidak 🔤 2	
Poor vision, colour blind Gangguan persendian	Ya 🗌	Tidak 🗌 2	
Joint pain/ swelling Berat badan turun	Ya 🗌	Tidak 🗾 2	
Weight loss	Ya 🗌	Tidak 📃 2	
Other, specify	Ya 🗌	Tidak 🔤 2	
Other, specify			
Bagain 5 : Pendapatan, Biaya Perawatan K Part 5: Income, Health care a		an Biaya Perja	lanan
24. Haruskah anda mengeluarkan uang unt datang ke klinik pada hari ini ?		Ya 🗋	Tidak 📃 2
Did you spend money to come to the clinic / hopsital today? Jika ya: 24a. Transportasi Transport			Rp
24b. Makanan & minuman Food or drink			Rp
24c. Waktu kerja terpotong Time off work	-		Rp
24d. Biayan pengobatan Medical expenses	-		Rp
25. Berapa jarak rumah /tempat tinggal anda dari k How far is your home from the clnic / hospital?	dinik?		km
di klinik ini ?	utan umum		Walk Private car Public transport other
27. Berapa lama waktu yang dibutuhkan untuk sar klinik?			jam
28. Berapa lama waktu yang dibutuhkan untuk per (termasuk menunggu untuk diperiksa, pemeriksaa dan pemeriksaan lain , menunggu obat)?			jam
Apakah anda didampingi oleh seseorang ke klinik	?	Ya 🗌 1	Tidak 🗌 2
28a. Jika "ya" berapa jumlah uang yang diper pendamping untuk satu jam?	oleh		Rp

Please remember to write time interview ended on cover page

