11 FINANCING

Financing has been secured (subject to ethical approval) from the following sources indicated in Table 4. Funding bodies have indicated that funds need to be spent by the dates indicated. In particular, major in-kind contributions have been committed by the out-going MALKON director, with the expectation of use of funds commencing prior to his departure in June 2008. Pending applications are listed, and further funding applications will be made as appropriate during subsequent years of the TB project.

Equipment	Cost \$ AUD
e.g. Niox Mino® Unit, Sensorpack and NO cylinder; lung	15 600
function testing accessories.	
Study medications	
Active and placebo L-arginine and vitamin D	11 392
On-site Specimen Collection And Processing (Timika)	
Blood, sputum	13 052
Off-site Specimen Collection And Processing (Australia))
e.g. PBMC, 1,25(OH)2D3, PTH, amino acids, sputum	Costs partly absorbed by NHMRC program
	grant
Travel and local study site wages	From 2008 ARC submission
Study Participant Incentives (travel costs, snack)	\$120 000

Table 3: Funding Requirements

Table 4: Funding Sources

Funding Source	Purpose	Time frame for use	Value \$ AUD

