Appendix 17: Cost-effectiveness analysis

Cost Effectiveness Analysis of L-Arginine or Vitamin D supplementation to improve Pulmonary TB treatment

The study will examine the cost-effectiveness of L-arginine or vitamin D supplementation in the clinical trial setting, compared with the cost effectiveness of unsupplemented TB treatment. Comparison of the cost effectiveness between the intervention and the control groups will permit policy decisions to be made regarding funding of these potential adjuvant TB treatments, if they are shown to be beneficial.

Hypotheses :

HO : Supplementation with L-arginine or Vitamin D are not cost-effective interventions to improve pulmonary TB cure rates.

H1 : Supplementation with L-arginine or Vitamin D are cost-effective interventions to improve pulmonary TB cure rates.

Method

Data collected directly from ADAPT study participants, and additional sources described below, will be used to conduct a cost-effectiveness analysis. The Cost Effectiveness analysis is used to compare the cost and effectiveness of the intervention group (with L-arginine or vitamin D supplementation) with cost and effectiveness for standard pulmonary TB treatment (without supplementation).

Cost Measurement :

Cost information will be collected from NTP reports, government and other official documents and from study participants following previously validated methods. This information will be used to count the following costs.

- 1. Total Health System Costs: The annual expenditure for NTP (including capital and recurrent costs), to calculate the cost per patient cured. A calculation will also be made about the costs of poor compliance in terms of relapse rates for TB (and hence more cases of TB to be treated) and the potential for the development of drug resistance (and hence more expensive treatments required).
- 2. Total Patient Costs: the total cost born by the patient from diagnosis, treatment and followup during the treatment. This includes transport costs, examinations fees, loss of income and other out of pocket expenditures.
- 3. Total Opportunity Costs: The total cost forgone by community and Community Health Workers caring for TB patients.
- 4. Costs of the intervention: The costs associated with the intervention (L-arginine or vitamin D) will be calculated by including all capital, recurrent and salary costs associated with this study.

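### Appendix 17 counts loss of income over the whole of treatment, but after baseline the weekly form asks about the patient's lost earnings only for the visit day and only in an if-yes branch about money spent

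*Protocol*

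**What the plan says.** Appendix 17 (Cost Measurement, item 2) defines total patient costs as running from diagnosis through treatment and follow-up. Of their content it says: "This includes transport costs, examinations fees, loss of income and other out of pocket expenditures". The cost-effectiveness formula in the same appendix puts total patient cost in the numerator of cost per cure, and the result is compared between intervention and control.

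The baseline form (Appendix 1, Section E) asks about occupation and daily pay. It then asks for the number of days the patient was "nable to perform all of your usual activities (work/school" (the first letter is lost in the text), and for the number of days on which only some activities were possible.

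The weekly form (Appendix 2) has a Part 5 whose legible heading begins "Part 5: Income, Health care a". Its item 24 reads "Did you spend money to come to the clinic / hopsital today? Jika ya: 24a. Transportasi Transport". Sub-items 24a to 24d follow the if-yes instruction, and one of them is "24c. Waktu kerja terpotong Time off work", recorded in rupiah. Items 25 to 28 cover distance, transport mode, travel time ("27. Berapa lama waktu yang dibutuhkan untuk sar klinik") and time at the clinic. Item 28a asks what a companion earns per hour ("berapa jumlah uang yang diper pendamping untuk satu jam").

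**The concern.** The reason given for testing these adjuvants includes a shorter illness with less disability (section 1.2.1), and section 1.2 links the economic burden of TB to its occurrence in the productive years of life. Days of work regained are therefore a main route by which either supplement could lower patient cost. The protocol lists loss of income as a cost to be counted, but its follow-up instrument does not ask about days lost to illness. It asks about visit-day earnings only within a branch opened by a question about spending.

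At stake is whether the cost comparison can show an arm difference in income lost to illness. An analysis plan cannot repair this later, because the data would not have been collected.

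**Working it through.** The protocol states no figure to reproduce here. The check is a comparison of the forms with the cost definition, plus a count of form days.

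**What each instrument can supply on the patient's own lost income**
- *Baseline form, Section E:* daily pay, days with no usual activity, days with partial activity. Asked once, at enrolment, before any treatment effect is possible.
- *Weekly form, item 24c:* rupiah lost through time off work. It belongs to the question about coming to the clinic today, so it covers that visit only, and it is reached through the if-yes branch on money spent.
- *Weekly form, items 27 and 28:* travel and clinic hours, asked of everyone. Multiplied by baseline pay, they could approximate the cost of attending. They say nothing about days lost to illness.
- *Weekly form, item 28a:* a companion's earnings, not the patient's.
- *Respiratory questionnaire, item 10 (Appendix 16), at weeks 0, 4, 8 and 24:* whether chest trouble stopped or affected work, as a category, without days or money.
- *Other Appendix 17 sources:* national programme reports and official documents cannot give an individual participant's lost workdays.

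Part of the symptom list in the weekly form (item 23) is broken in the text, but the item numbering up to 28 leaves no place for a separate days-unable question.

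**Coverage in time**
- Scheduled weekly forms: weeks 0 to 8 (9 forms) plus weeks 12, 16, 20 and 24 (4 forms) = 13 form days.
- Treatment period: 24 weeks × 7 = 168 days.
- Share of days on which any lost-earnings item is scheduled: 13 / 168 = 7.7%. No item covers the remaining 92%.

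**Illustration of the missing component (assumed patients)**
Two wage earners return to work at week 4 and week 16. Both walk to the clinic and spend nothing. If item 24 is answered No, 24c is skipped and both record zero lost income. The true difference is 16 − 4 = 12 weeks, or 84 calendar days: 12 × 5 = 60 working days at five days a week, 12 × 6 = 72 at six. The forms would show no difference in lost earnings.

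**Illustration of the if-yes branch (assumed values)**
At half a working day lost per form visit, 13 × 0.5 = 6.5 days. If 30%, 50% or 70% of visits involve no spending and 24c is then skipped, the form captures 6.5 × 0.7 = 4.55, 6.5 × 0.5 = 3.25 or 6.5 × 0.3 = 1.95 days. The half day and the shares are not in the protocol. They show how the branch works and do not estimate its effect in this trial.

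**The case against.** The best counter-argument is that Appendix 17 can be read narrowly. Its hypotheses concern cost per cure, faster recovery enters through the effectiveness measures (time to sputum conversion, clinical improvement), and loss of income is listed beside transport and examination fees. On that reading it might mean only earnings lost through attendance, which items 27 and 28 with baseline pay could approximate. The reading is possible, but it fits poorly with a patient cost defined over the whole span from diagnosis to follow-up, and with a baseline form that already asks for days lost to illness. The appeal to previously validated methods does not help, since no other participant cost form is shown.

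Three other points stand and limit the concern.

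1. A reader might infer that the comparison cannot register any patient-level saving. The form does not support that. Transport mode, medical expenses and companion earnings are recorded, and each can change with recovery or side effects. One component is missing, not all of them.
2. A reader might infer that the planned output in Table 5 on the economic burden of TB in Papua has the same gap. That output sits in a separate row from the trial's own cost-effectiveness paper, with no stated data source, so this cannot be shown.
3. A reader might infer that everyone who walks, or whose travel the study supports, loses item 24c. The form is completed by an interviewer and lists time off work among the things spent, so a patient who lost wages could be recorded as Yes. The budget line "Study Participant Incentives (travel costs, snack" does not say whether travel is prepaid or reimbursed. The effect of the branch depends on how interviewers use it. The restriction of 24c to the visit day does not.

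**Conclusion.** The point holds for one cost component. Appendix 17 counts loss of income through treatment and follow-up, but after baseline the forms record the patient's own lost earnings only for visit days and only within the if-yes branch on spending. Income lost to illness during treatment is not measured by arm. How much is missed cannot be derived from the protocol. It depends on how many patients earn a wage, how long they are off work and whether the adjuvants shorten that time. The day counts above are illustrations only.

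The consequence is confined to the economic analysis, which the Executive Summary lists as a related study. No primary or secondary outcome in section 4 is affected. The change is still worth making before data collection, because it is cheap then and the missing data cannot be recovered afterwards.

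**What to change.** 1. **Appendix 2, item 24c:** take it out of the if-yes branch and ask it of every patient, whatever the answer to item 24.
2. **Appendix 2, new items:** repeat the two baseline questions (items 28 and 29: days unable to do all, and days able to do only some, usual activities) at every scheduled form after week 0, that is weeks 1 to 8, 12, 16, 20 and 24, with recall since the last form. This covers 8 × 1 + 4 × 4 = 24 weeks. Asking only at weeks 4, 8 and 24 with the same recall would cover 1 + 1 + 4 = 6 of 24 weeks.
3. **Appendix 17:** define loss of income as full days lost × baseline daily pay, plus partial days × a stated fraction of daily pay (with a sensitivity range), plus 24c only for visits on days not already counted as lost. The last condition avoids double counting.

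The cost is about a minute more per interview, with no new staff or procedure. There will be some recall error over the four-week intervals after week 8.
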